NCI Protocol #: NCT04197310

DF/HCC Protocol #: 19-403

TITLE: Phase II trial of cabozantinib in combination with nivolumab for advanced carcinoid tumors

Coordinating Center: Dana-Farber Cancer Institute/ Harvard Cancer Center

Principal Investigator (PI): [name]
Dana-Farber Cancer Institute
[contact]

Other Investigators: [name], MPH
Dana-Farber Cancer Institute
[contact]

[name]
Boston Medical Center
[contact]

Statistician:
[name]
Massachusetts General Hospital
[contact]

Project Manager:
[name]
Dana-Farber Cancer Institute
[contact]

Responsible Research Nurses:
[name]
Dana-Farber Cancer Institute
[contact]

[name]
Dana-Farber Cancer Institute
[contact]

[name]
Dana-Farber Cancer Institute
[contact]

NCI-Supplied Agent(s): N/A

Other Agent(s): Cabozatinib – Exelixis; Nivolumab – Bristol-Myers Squibb

IND #: 144470

IND Sponsor: [name]

Protocol Type / Version # / Version Date: Version #6.0 / 20-May-2022

SCHEMA

Diseases:

Well-differentiated
Neuroendocrine Tumors of
non-pancreatic (i.e,
carcinoid) origin

Treatment:

**Nivolumab intravenously every 2 weeks
AND
Cabozantinib orally daily
28 day cycle**

Stage I: safety run-in (N= 18);

If more than 3 patients
demonstrate response measured
by RECIST 1.1 criteria then,
Stage II: expansion (N= 17)

TABLE OF CONTENTS

1	OBJECTIVES	8
1.1	Study Design	8
1.2	Primary Objective(s)	8
1.3	Secondary Objective(s)	8
1.4	Exploratory Objective(s)	8
2	BACKGROUND	9
2.1	Introduction	9
2.2	Rationale	10
2.3	IND Agent(s)	11
2.4	Correlative Studies Background	11
3	PARTICIPANT SELECTION	13
3.1	Eligibility Criteria	13
3.2	Exclusion Criteria	15
3.3	Inclusion of Women and Minorities	17
4	REGISTRATION	18
4.1	General Guidelines for DF/HCC Institutions	18
4.2	Registration Process for DF/HCC Institutions	18
4.3	General Guidelines for Other Investigative Sites	18
4.4	Registration Process for Other Investigative Sites	18
5	TREATMENT PLAN	19
5.1	Treatment Regimen	19
5.2	Pre-Treatment Criteria	20
5.3	Agent Administration	21
5.4	General Concomitant Medication and Supportive Care Guidelines	21
5.5	Criteria for Taking a Participant Off Protocol Therapy	25
5.6	Duration of Follow Up	27
5.7	Criteria for Taking a Participant Off Study	27
6	DOSING DELAYS/DOSE MODIFICATIONS	27
6.1	Dosing/Delays/Omission/Modification	27
6.2	Dose Levels	28
6.3	Hematologic Toxicities	28
6.4	Diarrhea/Colitis	29
6.5	Hepatobiliary Disorders	30
6.6	Elevated Amylase and/or Lipase	32
6.7	Fatigue, Anorexia and Weight loss Disorders	32

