16.2 Sample Size, Accrual Rate and Study Duration

The primary objective of this study is to investigate the safety and tolerability of the combination of cabozantinib and nivolumab. Based on the results of a phase II trial of cabozantinib as monotherapy for patients with advanced carcinoid and pancreatic NET and other trials examining anti-PD-1 agents in patients with other malignancies not selected by PD-L1 status, a true objective response rate (ORR) of 10% or less would not be of clinical interest and represents the null hypothesis of this study. A true rate of 30% would be considered a clinically meaningful level of response. The sample size for this study was chosen to have 95% power to declare the combination effective at this rate with a one-sided Type 1 error of no more than 5%.

Using a Simon's two-stage design, 18 patients will be enrolled in the first stage. If in this first stage there are at least 3 patients with an objective response (ORR), accrual will continue to the second stage where an additional 17 patients will be enrolled. If there are at least 7 patients with an objective response among the total 35 patients, the regimen will be considered worthy of further study.

If the true response rate is 10%, the chance the regimen is declared worthy of further study is less than 5% (exact alpha = 0.047). If the true response rate is 30%, the chance that the regimen is declared worthy of further study is 95%

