16.4 Interim Monitoring Plan

If in the first stage there are at least 3 patients with an objective response (ORR), accrual will continue to the second stage where an additional 17 patients will be enrolled.

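### The Schema requires at least 4 responders among 18 to open stage 2, but Sections 16.2 and 16.4 require at least 3; the Schema rule would lower power from 90.2% to 81.8%

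*Combined protocol and SAP*

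**What the plan says.** The Schema at the front of the protocol describes "Stage I: safety run-in (N= 18"), then sets the condition "If more than 3 patients" respond by RECIST 1.1, then "Stage II: expansion (N= 17"). Read literally, expansion needs 4 or more responders.

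Section 16.2 states: "Using a Simon's two-stage design, 18 patients will be enrolled in the first stage". It continues: "If in this first stage there are at least 3 patients with an objective response (ORR), accrual will continue to the second stage", with 17 more patients. Section 16.4, the Interim Monitoring Plan, repeats the rule: "If in the first stage there are at least 3 patients with an objective response (ORR), accrual will continue to the second stage". In both places expansion needs 3 or more responders.

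The final criterion appears in Section 16.2 only: "If there are at least 7 patients with an objective response among the total 35 patients", the regimen is judged worth further study. The same section sets the null ("a true objective response rate (ORR) of 10% or less would not be of clinical interest and represents the null hypothesis"), takes 30% as the rate of interest, and reports an exact alpha of 0.047 and power of 95%.

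Section 16.1 says that enrolment expands if the interim objectives are met. It gives no number and does not say which statement governs.

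**The concern.** Both statements describe the same stages (18 then 17) and the same endpoint, RECIST 1.1 response. They differ by one responder, and that responder decides the outcome: with exactly 3 of 18, the Schema closes the trial and Section 16 enrols 17 more patients.

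This is the only interim rule in the plan with a numerical response threshold. A team working from the Schema could close a trial that the design meant to continue. A team following Section 16 with 3 of 18 would be acting against another part of the approved protocol. Either way, the choice of threshold would be made after the responses were known, which is difficult to defend.

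The disputed result is also a realistic one. Section 2.1.2 reports 6 responses in 41 carcinoid patients on cabozantinib alone, about 15%. Three of 18 is 16.7%.

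**Working it through.** **Inputs.** Stage 1 size n1 = 18 and stage 2 size n2 = 17 (Schema; Section 16.2). Final success needs at least 7 of 35 (Section 16.2). Null rate 10%, alternative 30% (Section 16.2). Stage 1 cut-off a = 3 (Sections 16.2 and 16.4) or a = 4 (Schema).

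**Formula.** With X1 ~ Bin(18, p) and X2 ~ Bin(17, p), independent,

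P(success) = Σ over x ≥ a of P(X1 = x) × P(X2 ≥ 7 − x).

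This is alpha at p = 0.10 and power at p = 0.30.

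**Step 1: the plan's own figures, with a = 3.**

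| X1 | Contribution at p = 0.10 | Contribution at p = 0.30 |
|---|---|---|
| 3 | 0.1680 × 0.0826 = 0.0139 | 0.1046 × 0.7981 = 0.0835 |
| 4 | 0.0700 × 0.2382 = 0.0167 | 0.1681 × 0.9226 = 0.1551 |
| 5 | 0.0218 × 0.5182 = 0.0113 | 0.2017 × 0.9807 = 0.1978 |
| 6 | 0.0052 × 0.8332 = 0.0044 | 0.1873 × 0.9977 = 0.1869 |
| ≥ 7 | 0.0012 | 0.2783 |
| Total, unrounded terms | **0.0474** | **0.9016** |

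The stated alpha of 0.047 reproduces. The stated power of 95% does not: the exact value is 90.2%.

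**Step 2: the Schema rule, a = 4.** Drop the X1 = 3 row.

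- Alpha: 0.0474 − 0.0139 = 0.0335.
- Power: 0.9016 − 0.0835 = 0.8181.

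**Step 3: which rule the design was calculated from.** With the final criterion held at 7 of 35, stage 1 cut-offs of 2, 3 and 4 give alpha 0.0537, 0.0474 and 0.0335. Only 3 matches the stated 0.047.

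**Step 4: probability of stopping at stage 1.**

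| Rule | p = 0.10 | p = 0.30 |
|---|---|---|
| At least 3 (stop at 0–2) | 0.734 | 0.060 |
| At least 4 (stop at 0–3) | 0.902 | 0.165 |

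**Step 5: how often the rules disagree.** P(X1 = 3) = C(18,3) p³ (1 − p)¹⁵, with C(18,3) = 816. This is 0.168 at p = 0.10, 0.230 at p = 0.20 and 0.105 at p = 0.30.

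**Step 6: what is lost in that case.** A trial that continues from 3 of 18 needs at least 4 more responders among 17. At p = 0.30 that has probability 0.798. The product 0.1046 × 0.798 = 0.0835 is the whole power difference between the rules.

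**The case against.** The Schema is a one-page summary. The operative rule sits in the statistical section, is stated twice in the same terms, and is supported by the exact alpha, so a statistician running the interim would work from Section 16. The Schema error also cannot inflate false positives, because it lowers alpha to 0.034. Harm needs two things together: the team follows the summary, and exactly 3 of 18 respond (10.5% at a true rate of 30%). These points limit the expected harm. They do not remove a contradiction on a go/no-go threshold.

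A second objection concerns the size of the power loss, and it stands as a matter of presentation. The only power figure in the plan is 95%, so quoting 82% alone would suggest a 13-point loss. The loss due to the Schema wording is 90.2% − 81.8%, about 8.3 points before rounding. The gap between 95% and 90.2% is a separate error in Section 16.2. Correcting the Schema restores the stated alpha but not the stated power.

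Third, the 18-patient interim also covers tolerability, there is a safety check after 6 on-treatment biopsies, and the data and safety monitoring committee reviews the trial. None of these carries a numerical go/no-go rule, so none settles what happens at 3 of 18.

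**Conclusion.** The contradiction is real, and the Schema is the text in error. Section 16.2 and Section 16.4 agree with each other, and only their rule gives the stated alpha of 0.047. Following the Schema would lower power at a 30% response rate from 90.2% to 81.8%, lower alpha from 0.047 to 0.034, and raise the chance of a wrongful stage 1 stop from 6.0% to 16.5%. The two rules give opposite decisions with probability between 10.5% and 23.0% at true response rates of 10%, 20% and 30%.

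The figures assume independent responses with a common rate, exactly 18 and 17 patients counted in the two stages, and the final criterion of 7 in 35 unchanged. Because the point affects the response-based interim decision and can be settled from the document itself, it must be fixed before the interim count is acted on.

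**What to change.** Reword the Schema condition so that stage 2 (N = 17) opens if at least 3 of the first 18 patients have a confirmed objective response by RECIST 1.1. The change from more than 3 to at least 3 is the essential one and matches Sections 16.2 and 16.4. The word confirmed comes from the definition of the primary endpoint in Section 16.1.1. The stage 1 rules in 16.2 and 16.4 do not repeat it, so it should be added there too; it affects when the interim count is final, since Section 11.1 places the confirmatory scan 8 weeks, and not less than 4, after the first response.

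The cost is one line in the Schema and, for consistency, one word in each of two sections. Sample size, treatment and the final criterion do not change. The 95% power statement in Section 16.2 should be corrected separately.

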1 OBJECTIVES

1.1 Study Design

This is an open-label, single-arm, phase 2 study of nivolumab given in combination with cabozantinib. Nivolumab will be administered every two weeks at a dose of 240 mg given intravenously. Cabozantinib will be administered orally, once daily at a dose of 40 mg.

1.2 Primary Objective(s)

To evaluate the efficacy of cabozatinib in combination with nivolumab, as defined by objective response rate (ORR) according to RECIST 1.1, in patients with advanced carcinoid tumors.

1.3 Secondary Objective(s)

- 1.3.1 To evaluate the safety and tolerability of cabozantinib in combination with nivolumab in patients with advanced carcinoid tumors.
- 1.3.2 To evaluate the ORR of cabozantinib in combination with nivolumab in patients with advanced carcinoid tumors according to immune-related response criteria (irRC).
- 1.3.3 To evaluate the duration of response in patients with advanced carcinoid tumors receiving the combination of cabozantinib and nivolumab.
- 1.3.4 To evaluate progression-free survival of patients with advanced carcinoid tumors treated with the combination of cabozantinib and nivolumab.
- 1.3.5 To evaluate overall survival of patients with advanced carcinoid tumors treated with the combination of cabozantinib and nivolumab.

1.4 Exploratory Objective(s)

- 1.4.1 To explore whether baseline tumor immune cell infiltration and PD-L1 and PD-L2 staining correlates with response to therapy.
- 1.4.2 To explore whether changes in circulating immune cell profile correlates with response to therapy.
- 1.4.3 To explore whether changes in the level of angiogenic and inflammatory blood biomarkers during therapy correlate with efficacy of therapy.

2 BACKGROUND

2.1 Introduction

Neuroendocrine neoplasms are a relatively rare heterogeneous group of malignancies. These tumors arise from neuroendocrine cells located throughout the body. In current clinical practice neuroendocrine neoplasms are divided into two groups based on clinical behavior, histology, and proliferation rate: well differentiated (low grade to intermediate grade) neuroendocrine tumors (NET) and poorly differentiated (high grade) neuroendocrine carcinomas (NEC). This dichotomization is clinically relevant for therapeutic and prognostic purposes, though imprecise as the behavior (metastatic potential, local invasion, recurrence after resection) can be very heterogeneous. Furthermore, there are distinctions in the management of well-differentiated neuroendocrine tumors arising in the pancreas versus non-pancreatic primary sites, including organs such as thymus, lung, and the gastrointestinal tract. Well-differentiated neuroendocrine tumors arising in non-pancreatic sites have historically been classified as carcinoid tumors. Current therapeutic options for carcinoid tumors include somatostatin analogs, everolimus, and the radiolabeled somatostatin analog lutetium-177 dotatate. These therapies have been shown to improve progression-free survival for patients with advanced stage disease, but the benefit is finite. As such, newer therapeutic options are needed to manage this very heterogeneous disease.

2.1.1 The PD-1/PD-L1 pathway in cancer

The role of intact immune surveillance in controlling neoplastic transformation and growth has been well-described. (Restifo) There is recent evidence demonstrating a correlation between tumor-infiltrating lymphocytes (TILs) in cancer tissue and clinical outcomes. (Mlecnik) The PD-1 receptor ligand interaction is a major pathway hijacked by tumors to suppress immune control. The normal function of PD-1, expressed on the cell surface of activated T-cells under healthy conditions, is to down-modulate unwanted or excessive immune responses, including autoimmune reactions. PD-1 is an Ig superfamily member related to CD28 and CTLA-4 which has been shown to negatively regulate antigen receptor signaling upon engagement of its ligands (PD-L1 and/or PD-L2). PD-1 is expressed on activated lymphocytes including peripheral CD4+ and CD8+ T-cells, B-cells, Tregs, natural killer cells, and a subset of macrophages and dendritic cells. The ligands for PD-1 (PD-L1 and PD-L2) are constitutively expressed or can be induced in a variety of cell types. PD-L1 serves to dampen unwarranted T-cell function in peripheral tissues and PD-L2 controls immune T-cell activation in lymphoid organs. Most healthy tissues express few PD-L1 ligands, a variety of cancer demonstrate an abundant level, thus suggesting that the PD-1/PD-L1 pathway plays a critical role in tumor immune evasion and is therefore considered an attractive target for therapeutic intervention. (Intlekofer)

The PD-1/PD-L1 pathway in neuroendocrine tumors

The new generation of immunotherapy treatment, check-point inhibitors, has not yet been proven to be effective in patients with NETs. Prior analysis of interferon in NET, a classic immune-modulatory drug, demonstrated an ability to stimulate T-cell function, control the secretion of tumor products and inhibit tumor growth by activation of the T-cell response against the tumor and angiogenesis inhibition in NETs (Oberg). Efforts to better characterize the

immune response in NET have been undertaken, and several studies have demonstrated an association between expression of PD-L1, presence of TILs, and clinical outcome. Lamarca and colleagues recently demonstrated that 30% of a 109 patient cohort of SINETs showed expression of PD-L1 within tumor cells and/or TILs, together with a high rate of TIL presence. In this cohort, 17.2% demonstrated a concomitant presence of CD8+ lymphocyte aggregate and PD-L1 expression. (Lamarca) Other studies have demonstrated similar results, with high grade or well differentiated grade 3 NETs consistently demonstrating a higher expression of PD-L1 when compared to grade 1 or 2 NET. (Lamarca, Cavalcanti, da Silva). In contrast, in another cohort of patients with NET, including 64 with small intestinal NET (SINET) and 21 with pancreatic NET, no membranous expression of PD-L1 was identified in the SINETs group, and 11% was noted in the PNET cohort. Both groups, however, showed T-cell tumor infiltrate. (da Silva).

The therapeutic use of immune checkpoint inhibitors and NETs is currently under investigation. The results of the first completed study was presented at the ESMO 2017 Annual Conference. The Keynote-028 study evaluated the use of pembrolizumab for patients with PD-L1 positive advanced carcinoid or pancreatic NET. The study screened 276 patients for the presence of PD-L1; 36% were positive (carcinoid N=25; pancreatic NET N=16). Three carcinoid patients (12%; 95% CI, 3-31%) and one PNET (6%; 95% CI, 0-30%) had an objective response; stable disease rates were 60% (n=15) and 88% (n=14) respectively. Duration of response ranged between 6.9 to 11.1 months for the carcinoid responders; and 17.6 months for the PNET responder. (Mehnert) Other clinical trials are currently evaluating the role of checkpoint inhibitors and focusing on NETs that are both well-differentiated and poorly differentiated, and studies are also evaluating checkpoint inhibitors in combination with other immunomodulatory agents (NCT03167853, NCT02955069, NCT03095274, NCT03074513).

2.1.2 Cabozatinib in carcinoid tumors

Cabozantinib is an orally administered drug that is classified as a small-molecule tyrosine kinase inhibitor (TKI). It is a reversible competitive inhibitor of tyrosine kinase receptors including VEGFR2, MET, AXL, and RET. Cabozantinib has demonstrated efficacy in advance renal cell carcinoma and metastatic medullary thyroid cancer. (Choueiri, Brose) We recently demonstrated in a phase II trial of patients with advanced carcinoid and pancreatic neuroendocrine tumors (NET) that treatment with single agent cabozantinib was associated with encouraging response rates and progression-free survival [2]. The objective response rate, as measured by RECIST 1.1, was 15% in patients with both carcinoid tumors (6/41) and pancreatic NET (3/20). (Chan) The CABINET study, a randomized, phase III placebo-controlled clinical trial, is currently open to enrollment and will further evaluate the efficacy of cabozantinib in patients with advanced pancreatic NET and carcinoid tumors previously treated with everolimus (NCT03375320).

2.2 Rationale

Although NET is not typically considered to be an immunogenic malignancy, an increasing body of preclinical and clinical evidence suggests that modulation of the immune system can influence disease outcome. In particular, anti-PD-1/PD-L1 antibodies have demonstrated clinical efficacy,

and two PD-1 inhibitors (nivolumab and pembrolizumab) are FDA approved for the treatment of multiple cancer types. (Brahmer) Although immune checkpoint inhibitors have made an enormous impact on therapeutic strategies, there remain many tumor types and subsets of tumor types in which therapeutic benefit has not been clearly demonstrated. This suggests that there may be additional immunosuppressive factors causing resistance to immunotherapy, and other agents must be added to anti-PD-1/PD-L1 treatment in order to enhance the benefit of immunotherapy.

Treatment with cabozantinib has been associated with immunomodulatory changes. In a phase II study of patients with triple negative breast cancer, for example, significant and persistent increases in circulating CD3+ T-lymphocytes were observed after treatment with cabozantinib, driven primarily by increase in CD8+CD4–cytotoxic T-lymphocytes. (Tolaney) Moreover, there was a significant decrease in circulating CD14+ monocytes, an immunosuppressive myeloid-derived population. These changes in circulating immune cells provides rationale for combining cabozantinib with immune checkpoint inhibitors as an innovative treatment strategy. Similar treatment strategies are being proposed in other malignancies, including urothelial and genitourinary malignancies (NCT02496208) and renal cell carcinoma (NCT03141177).

Neuroendocrine tumors provide another ideal platform upon which to perform such a study. Given the single agent activity of cabozantinib in NET, and the potential immunomodulatory potential of cabozantinib, we propose a phase II study to evaluate the antitumor activity of cabozantinib plus nivolumab (anti-PD-1 monoclonal antibody) in patients with advanced carcinoid tumors.

2.3 IND Agent(s)

- 2.3.1 Cabozatinib – refer to the Investigator’s Brochure (IB)/ approved labeling for detailed background information.
- 2.3.2 Nivolumab - refer to the Investigator’s Brochure (IB for detailed background information.

2.4 Correlative Studies Background

The importance of the tumor microenvironment and immune surveillance in the natural history of cancer has proved to be significant in our therapeutic strategy. However, less than half of patients with solid tumors will derive benefit from these drugs alone. (Ribas) Thus, it is imperative to examine the mechanisms of antitumor immunity evasion in the tumor microenvironment to direct immunotherapy treatment. This effort can be moved forward by the discovery and validation of prognostic and predictive biomarkers.

Although multiple cancers have demonstrated a sensitivity to immunotherapy, there are subsets that do not appear to respond. The lack of a significant T-cell infiltrate and low expression of immune checkpoint molecules may explain the reason that certain non-inflamed tumor phenotypes are associated with de novo resistance to anti-PD-1 / anti-PD-L1 drugs. For this group of patients, therapeutic strategies that promote an increase in cytotoxic T-cell infiltration,

such as anti-angiogenic therapies, may be relevant to successfully overcoming T-cell exclusion and improve the likelihood of benefit of PD-1 blockers.

Tolaney and colleagues recently published their experience in triple negative breast cancer with single-agent cabozantinib. Although the study did not meet its pre-specified endpoint, there were notable notable biomarker changes after treatment with cabozantinib which included: significant and durable increases in plasma placental growth factor, vascular endothelial growth factor (VEGF), VEGF-D, stromal cell-derived factor 1a, and carbonic anhydrase IX, and circulating CD3+ cells and CD8 + T lymphocytes, and decreases in plasma soluble VEGF receptor 2 and CD14+ monocytes (all $p < .05$). There was a significant increase in the fraction of circulating CD3+ cells and CD3 + CD4-CD8+ T lymphocytes at days 22 and 64 ($p = .04$ and $p = .01$, respectively), and a decrease in percentage of CD14+ monocytes at days 22 and 64 ($p = .01$). (Tolaney) Although none of these findings, except baseline soluble MET levels, were associated with outcome measures, this is the first description of cabozantinib induced modulation of immune cells in the clinical setting. We propose analysis of potential biomarkers of cabozantinib and nivolumab activity in carcinoid and the impact on the immune environment. We intend to explore changes in angiogenic/inflammatory biomarkers during treatment, the characteristics of potential immune biomarkers and expression of immune checkpoint molecules, and TILs to explore the activity of cabozantinib and nivolumab in carcinoid tumors.

